3.2 Exclusion Criteria

Participants who do not fulfill the criteria as listed in Section 3.1 above, are ineligible. Additionally, the presence of any of the following conditions will exclude a participant from study enrollment:

- 3.2.1 Participants who have received any other investigational agents within the 4 weeks prior to enrollment. Concurrent radiation therapy is not permitted, except palliative (limited-field) radiation therapy, if all of the following criteria are met:
 - 1) Repeat imaging demonstrates no new sites of bone metastases.
 - 2) The lesion being considered for palliative radiation is not a target lesion.
- 3.2.2 Participants with known brain metastases or leptomeningeal metastases must be excluded unless they qualify for enrollment as described below because of poor prognosis and concerns regarding progressive neurologic dysfunction that would confound the evaluation of neurologic and other AEs. Participants with brain metastases are permitted if metastases have been treated and there is no magnetic resonance imaging (MRI) evidence of progression for at least 4 weeks or more after treatment is complete and within 4 weeks prior to the first dose of nivolumab

administration.

- 3.2.3 History of allergic reactions attributed to compounds of similar chemical or biologic composition to ipilimumab, nivolumab, or other agents used in study, or history of severe hypersensitivity reaction to any monoclonal antibody.
- 3.2.4 Participants should be excluded if they have a condition requiring systemic treatment with either corticosteroids (>10 mg daily prednisone equivalents) or other immunosuppressive medications within 2 weeks of study drug administration. These drugs may interfere with the activity of ipilimumab and nivolumab if administered at the time of the first ipilimumab dose. Inhaled or topical steroids and adrenal replacement doses ≤10 mg daily prednisone equivalents are permitted in the absence of active autoimmune disease. Participants are permitted to use topical, ocular, intra-articular, intranasal, and inhalational corticosteroids (with minimal systemic absorption). Physiologic replacement doses of systemic corticosteroids are permitted, even if ≥10 mg/day prednisone equivalents. A brief course of corticosteroids for prophylaxis (e.g., contrast dye allergy) or for treatment of non-autoimmune conditions (e.g., delayed-type hypersensitivity reaction caused by contact allergen) is permitted. Use of anabolic steroids is permitted.
- 3.2.5 Participants with clinical or radiographic evidence of pancreatitis are excluded.
- 3.2.6 Uncontrolled intercurrent illness including, but not limited to, ongoing or active infection, symptomatic congestive heart failure, unstable angina pectoris, cardiac arrhythmia, or psychiatric illness/social situations that would limit compliance with study requirements.
- 3.2.7 Participants should be excluded if they have had prior treatment with an anti-PD-1, anti-PD-L1, anti-PD-L2, anti-CTLA-4 antibody, or any other antibody or drug specifically targeting T cell co-stimulation or immune checkpoint pathways. Prior immune modulating therapy including vaccines may be eligible. Prior immune events must be evaluated and the risk for new events, which may represent continued sub-clinical disease or a new process at previously damaged site or immune potentiation (e.g., ipilimumab followed by IL2 causing bowel perforation, ipilimumab followed by IDO inhibitor resulting in clinical hypophysitis). Please keep in mind that inflammatory events may occur weeks to months following the last dose of ipilimumab and possibly nivolumab.

Assessment of potential effects of prior therapy should include:

Immune status

Organ damage

Risk of autoimmunity

Immunopotentiation

- 3.2.8 The participant has not recovered to baseline or CTCAE ≤ Grade 1 from toxicity due to all prior therapies except ≤ Grade 2 alopecia, neuropathy, and other non-clinically significant AEs.
- 3.2.9 The participant has a primary brain tumor.

3.2.10	Participant has \geq grade 2 diarrhea (participants with grade 1 diarrhea are eligible provided stool for ova/parasites and stool cryptosporidium studies are negative).
3.2.11	Opportunistic infection within the last 3 months.
3.2.12	Autoimmune disease: Participants with active autoimmune disease or history of autoimmune disease that might recur, which may affect vital organ function or require immune suppressive treatment including systemic corticosteroids, should be excluded. These include but are not limited to participants with a history of immune-related neurologic disease, multiple sclerosis, autoimmune (demyelinating) neuropathy, Guillain-Barré syndrome, myasthenia gravis; systemic autoimmune disease such as SLE, connective tissue diseases, scleroderma, inflammatory bowel disease (IBD), Crohn's, ulcerative colitis, hepatitis; and participants with a history of toxic epidermal necrolysis (TEN), Stevens-Johnson syndrome, or phospholipid syndrome should be excluded because of the risk of recurrence or exacerbation of disease. Participants with vitiligo, endocrine deficiencies including thyroiditis managed with replacement hormones including physiologic corticosteroids are eligible. Participants with rheumatoid arthritis and other arthropathies, Sjögren's syndrome and psoriasis controlled with topical medication and participants with positive serology, such as ANA, antithyroid antibodies should be evaluated for the presence of target organ involvement and potential need for systemic treatment but should otherwise be eligible.
	Participants are permitted to enroll if they have vitiligo, type I DM, residual hypothyroidism due to autoimmune condition only requiring hormone replacement, psoriasis not requiring systemic treatment, or conditions not expected to recur in the absence of an external trigger (precipitating event).
3.2.13	Participants who have had evidence of C. difficile infection, active or acute diverticulitis, intra-abdominal abscess, GI obstruction and abdominal carcinomatosis, which are known risk factors for bowel perforation, should be evaluated for the potential need for additional treatment before coming on study.
3.2.14	cHL cohort only: history of allogeneic transplant.

3.3 Criteria for Solid Tumor Expansion and Lymphoma Cohorts

Inclusion and exclusion criteria for the solid tumor cohorts are the same as above, with the following rule for CD4 count based on tolerability in Phase I. If, participants with lymphocyte T CD4 count between $100-200/\text{mm}^3$ (Stratum 2) are shown to tolerate treatment in the Phase I dose de-escalation portion at the same dose level as those with CD4 counts $\geq 200/\text{mm}^3$ (Stratum 1), participants in the expansion cohort with CD4 counts $\geq 100/\text{mm}^3$ are permitted. Otherwise, the expansion is open to all solid tumor patients except those whose tumors are known not to respond to nivolumab (pancreas, prostate and MSS colon cancer). For the relapsed refractory HIV-cHL cohort, participants with CD4

count $\geq 100/\text{mm}^3$ are permitted.

3.4 Number of Participants to be Enrolled

3.4.1 Proposed sample size

This study will enroll a minimum of 4 participants and a maximum of 96 participants (see Section 10.2).

3.4.2 Accrual rate

Approximately two participants per month for Phase I, Stratum 1; approximately one participant per month for Phase I, Stratum 2. Approximately 2-3 participants per month for the combination therapy solid tumor expansion cohort and approximately 2-3 participants per month for the single agent solid tumor cohort (excluding those histologies not known to respond to single agent nivolumab, i.e., pancreas, prostate, MSS colorectal cancer). The cHL cohort will enroll approximately 3-4 patients per month.

3.5 Participant Enrollment Procedures

Sites must have this protocol approved by their Institutional Review Boards (IRB) and be registered for study participation with the AMC Operations and Data Management Center (ODMC) before they may enroll participants.

After an informed consent form has been signed by the participant and it has been determined that the participant is eligible, the participant must be registered on-line via the AMC AdvantageEDCSM Internet Data Entry System (AdvantageEDC). Enrollment and data collection will occur via the AMC Internet Data Entry System.

The participating site will ensure a participant meets all eligibility criteria prior to completing the protocol-specific eligibility checklist in AdvantageEDC for enrollment. Participants will be enrolled on-line via AdvantageEDC no more than 1 week prior to the initiation of treatment (enrollment 1 day prior to or on the day of treatment is strongly encouraged). It may take up to three business days for sites to receive nivolumab. Once the eligibility checklist is submitted, a system-generated confirmation email will be sent to the enroller upon successful completion of the participant enrollment. If the on-line system is inaccessible, the site should notify the AMC ODMC (via email at [contact] or via phone at [contact]) for further instructions.

4.0 TREATMENT PLAN

4.1 Treatment Design

Protocol agents will be administered on an outpatient basis. Reported AEs and potential risks for ipilimumab and nivolumab are described in Section 6.0. Appropriate dose modifications for ipilimumab and nivolumab are described in Section 5.0, Appendix X. No investigational or commercial agents or therapies other than those described below may be administered with the intent to treat the participant's malignancy.

Participants will be studied in separate strata. Stratum 1 will enroll participants with lymphocyte T CD4+ count above $200/\text{mm}^3$. Stratum 2 will enroll participants with lymphocyte T CD4+ count between $100\text{-}200/\text{mm}^3$. Enrollment on Stratum 2 will occur sequentially, initially in Stratum 1 at dose level 1, and then in Stratum 2 after Stratum 1 has completed and an MTD has been determined. Once the MTD is determined in each stratum, the MTD will then be studied in a dose expansion cohort of up to 12 participants. If the MTDs differ between the two strata, expansion cohorts of six participants each will be enrolled. An additional cohort of 12 participants with cHL and lymphocyte T CD4+ count $\geq 100/\text{mm}^3$ will be treated with single agent nivolumab. Lastly, an additional 24 participants with solid tumors will be treated with single agent nivolumab.

4.2 Dose De-Escalation Cohorts: Stratum 1 and Stratum 2

For Stratum 1, the study is a phase I dose de-escalation trial with a rolling six design to establish the MTD for single agent nivolumab and then the MTD for combination of ipilimumab and nivolumab. Since there are only two dose levels within each single and combination therapy, the design requires the full cohort of six participants to be enrolled unless two of the first three participants in that cohort experience a DLT, or if two or more participants in that cohort experience a DLT. In Stratum 1, two agents will be studied, initially nivolumab as a single agent (starting at Dose Level 1) and then the combination of ipilimumab and nivolumab (starting at Dose Level 2 or -2). After evaluating single agent nivolumab dosing, the next dose level will be 2 if dose level 1 is the MTD for single agent nivolumab or dose level -2 if dose level -1 is the single agent MTD. If 2 DLTs are experienced at Dose Levels 1 or 2, then one dose de-escalation (Dose Levels of -1 or -2, respectively) will be permitted according to the dose de-escalation schedule. Fixed doses will be administered according to the dosing schema in the treatment plan. The Phase I MTD for single agent or combination therapy is the dose level at which $\leq 1/6$ participants experience DLT, with the next higher dose having >2 participants encountering DLT (unless the MTD is the highest pre-specified dose level). The safety evaluation period is 6 weeks at a given dose level. No dose escalation will be allowed in an individual participant. and participants who have dose limiting AEs or disease progression will discontinue therapy. During the period for evaluating DLT, participants who withdraw from the study or do not complete the required cycles of treatment owing to reasons other than drugrelated AEs can be replaced. Participants will have blood drawn before each cycle for routine safety laboratory monitoring. All participants will be followed every 2 weeks for treatment administration, exam, toxicity, response, and compliance assessment for a minimum of 8 weeks and up to 92 weeks of treatment.

Table 1: Dose De-Escalation Schedule Stratum 1 and 2

Dose Level	Nivolumab* q2 wk x 46 doses	Ipilimumab**
Level -1	1 mg/kg	-
Level 1	3 mg/kg	-
Level 2	240 mg	1 mg/kg q 6 wk x 16 doses (day 1 of nivolumab cycles 1, 4, 7, 10, 13, 16, 19, 22, 25, 28, 31, 34, 37, 40, 43, and 46)
Level -2	1 mg/kg	1 mg/kg q 12 wk x 8 doses (day 1 of nivolumab cycles 1, 7, 13, 19, 25, 31, 37, and 43)

^{*}Doses are stated as exact dose in units (e.g., mg/m², mcg/kg, etc.) rather than as a percentage.

***Treatment will continue until documented disease progression, discontinuation due to toxicity, withdrawal of consent, or the study ends, up to 46 doses of nivolumab (with ipilimumab, if receiving).

NOTE: After evaluating single agent nivolumab dosing, the next dose level will be 2 if dose level 1 is the MTD for single agent nivolumab and dose level -2 if dose level -1 is the single agent MTD. It is also possible to de-escalate from dose level 2 to -2. Stratum 2 participants will not be allowed to escalate beyond the MTD for Stratum 1; one dose level de-escalation of the nivolumab and ipilimumab combination or to single agent nivolumab will be allowed based on the doses in the schema in the treatment plan.

NOTE: Participants treated on the cHL cohort and participants on the solid tumor expansion cohort of 24 participants will be treated at 240 mg.

These rules are based on concurrently enrolling up to six participants on the initial dose level (Dose Level 1). However, accrual will be suspended before enrolling the 4th-6th participants on a cohort to until safety has been evaluated in the first three participants, unless at least two participants on that cohort have completed the safety evaluation period without DLT.

- If, after completing the first six weeks for single agent nivolumab (Dose Level 1), none or one participant out of six exhibits a POSSIBLY, PROBABLY or DEFINTELY, study treatment-related DLT (i.e., ≤1/6 participants with DLT at that Dose Level 1; see Section 4.4), then the next cohort of participants will be treated at Dose Level 2.
- 2. However, if a second participant develops a study treatment POSSIBLY, PROBABLY or DEFINTELY related DLT, even if it is before there are six total participants on that level, then the single agent MTD has been exceeded and no additional participants should be added to this dose. A total of six participants should then be treated on the next lowest dose level (Dose Level -1) to ensure its tolerability and to better define the MTD. Thus, the MTD is defined as the highest assigned dose level at which ≤1/6 participants have a DLT. If ≥2 participants on level -1 experience a POSSIBLY, PROBABLY or DEFINTELY related DLT, the MTD will have been exceeded and no additional participants will be added at level -1 or receive combination therapy levels 2 or -2. If Dose Level -1 is the single agent MTD, then the next cohort of participants will be treated at Dose Level -2.

^{**}When the two drugs are administered, nivolumab will be administered first. Doses of intravenous nivolumab will be administered every 2 weeks up to 46 doses. Ipilimumab will be administered every 6 weeks on dose level 2 or every 12 weeks on dose level -2.

3. If, after completing first 6 weeks for combination of ipilimumab and nivolumab (Dose Level 2 or -2), 0/6 or ≤1/6 exhibits a POSSIBLY, PROBABLY or DEFINTELY, study treatment-related DLT then that dose level is the combination-agent MTD. If a second participant develops a study treatment POSSIBLY, PROBABLY or DEFINTELY related DLT, even if it is before there are six total participants on that level, then the combination-agent MTD has been exceeded and no additional participants should be added to this dose. A total of six participants should then be treated on the next lowest dose level (Dose Level -2 if not already at the lowest dose) to ensure its tolerability and to better define the MTD. If ≥2 participants on level -2 experience a POSSIBLY, PROBABLY or DEFINTELY related DLT, the MTD will have been exceeded and no additional participants will be added at level -2.

4.2.1 Dosing for Stratum 1

The study treatment consists of up to 46 intravenous (IV) infusions of nivolumab on day 1 of each 2-week cycle for the dose level -1 and 1 cohorts. For dose level 2, IV infusions of nivolumab are given on day 1 of each 2-week cycle and ipilimumab on day 1 every 6 weeks, i.e., every third cycle of nivolumab (cycles 1, 4, 7, etc.). For dose level -2, IV infusions of nivolumab are given on day 1 of each 2-week cycle, and ipilimumab is given on day 1 every 12 weeks, i.e., every sixth cycle of nivolumab (cycles 1, 7, 13, etc.).

Participants with an overall response of SD, PR, CR, or unconfirmed PD (refer to Section 9.1 for Response Evaluation Criteria in Solid Tumors (RECIST) Criteria at the scheduled response visits at week 8 and all subsequent visits day 1 of cycles 6 and 9 will be eligible to continue to receive study drug treatments provided that they also have an Eastern Cooperative Oncology Group (ECOG) performance status score of ≤ 2 , and did not have a DLT or other safety risk requiring discontinuation of the study drugs. Before dosing can continue after the day 1 of cycles 5 and each subsequent visit at which response is assessed (every 12 weeks thereafter), the results of the scheduled response assessments must be reviewed to determine, and document continued eligibility prior to administration of the study drugs.

Participants with an overall response of SD, PR, CR, or unconfirmed PD at the end of the first four cycles will continue treatment for up to a total of 46 cycles (refer to Section 9.1 for RECIST Criteria). Participants with confirmed PD after the first four cycles of therapy will discontinue the study drugs. Participants without evidence of confirmed progression after the first four cycles, with either a poor performance status (ECOG > 2) or toxicity requiring discontinuation of the study drugs will continue treatment until confirmed PD, requiring initiation of a new treatment.

4.2.2 Dosing Stratum 2

After review of AEs in Stratum 1, this will be followed by evaluation of nivolumab and ipilimumab in Stratum 2. Stratum 2 single agent dosing will begin after the MTD for Stratum 1 single agent therapy has been confirmed (dose level 1 or -1). After the Stratum 1 combination therapy MTD is determined (dose level 2 or -2), Stratum 2 will begin evaluation of combination therapy at that dose level. Up to six participants will be concurrently enrolled at the Stratum 1 MTD, following the dose de-escalation rules and treatment plan outlined above in Section 4.2 and 4.2.1. Stratum 2 participants will not be allowed to escalate beyond the MTD for Stratum 1; one dose level de-escalation of the nivolumab and ipilimumab combination or to single agent nivolumab will be allowed based on the doses in the schema in the treatment plan. The Phase I MTD is the dose level at which <1/6 participants experience DLT with the next higher dose having ≥2 participants encountering DLT (unless the MTD is the highest pre-specified dose level). No dose escalation will be allowed in an individual participant, and participants who have dose limiting AEs or disease progression will discontinue therapy. During the period for evaluating DLT, participants who withdraw from the study or do not complete the required cycles of therapy owing to reasons other than drug-related AEs can be replaced. During the first four cycles of treatment, participants will have blood drawn weekly for routine safety laboratory monitoring. Participants will then be followed every 2 weeks for treatment administration, exam, toxicity, response, and compliance assessment for a minimum of 8 weeks, and up to 92 weeks.

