4.2.3 Expansion Cohort in Solid Tumors and Lymphoma

An additional 24 participants with incurable solid tumors will be treated at the MTD, according to the treatment schedule defined above for each stratum. If the MTDs differ between the two strata, expansion cohorts of six participants each will be enrolled.

Another 24 participants with incurable solid tumors will be treated at single agent nivolumab 240 mg every 2 weeks. Only those histologies that are not known to respond to single agent nivolumab will be excluded (i.e., pancreas, prostate, MSS colorectal cancer, unless results from another clinical trial showing non-response in another tumor type become available in the future).

Participants with HL will be treated at the FDA approved flat dose of 240mg given every 2 weeks.

Participants with an overall response of SD, PR, CR, or unconfirmed PD at the end of the first four cycles of nivolumab will continue treatment for up to a total of 46 cycles of nivolumab (with ipilimumab if receiving dose level 2 or -2) (refer to Section 9.1 for RECIST Criteria and Section 9.3 for the 2017 response evaluation criteria in lymphoma (RECIL) Criteria for evaluating measurable disease in HIV-cHL).

Participants with a confirmed PD will discontinue the study drugs.

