4.6.4 Precautions

Combination therapy may result in unexpected toxicity especially in novel combinations with other immune modifying agents. A striking example in macaques is presented in Vaccari, *et al.* 2012.

Please note that while unproven, there is a suggestion that autoimmune events, including hepatitis, may occur more frequently at sites of metastases or prior injury.

Caution is advised when considering treatment with high dose IL-2 in participants who have previously been administered ipilimumab, particularly in participants who experienced ipilimumab-related diarrhea/colitis. Colonoscopy or sigmoidoscopy with biopsy may be advisable prior to IL-2 administration once the participant is no longer receiving ipilimumab.

Participants who have received ipilimumab may potentially develop autoimmune disease with subsequent therapy including the appearance of colitis, hypophysitis, or adrenal insufficiency.

4.7 **Duration of Therapy**

In the absence of treatment delays due to AE(s), treatment may continue 92 weeks of nivolumab (with ipilimumab, if receiving dose level 2 or -2) until one of the following criteria applies:

• The development of progression (confirmed PD by RECIST Criteria or PD by the KS evaluation criteria in Section 9.2 or per Section 9.3, utilizing the consensus RECIL (2017). Participants will remain on study treatment until progression is confirmed,

Pregnancy

- All WOCBP should be instructed to contact the investigator immediately if they suspect they might be pregnant (e.g., missed, or late menstrual period) at any time during study participation. Institutional policy and local regulations should determine the frequency of on study pregnancy tests for WOCBP enrolled in the study.
- o The investigator must immediately notify CTEP in the event of a confirmed pregnancy in a study participant.
- Intercurrent illness that prevents further administration of treatment.
- Unacceptable AE(s) which include the following (see also Section 6.0 and specific algorithms in Appendix X):
 - o Any grade 4 events except as noted below.
 - o Grade 3 drug-related autoimmune or inflammatory events including uveitis, pneumonitis, diarrhea, colitis, neurologic AEs, hypersensitivity reaction, or infusion reaction of any duration requires discontinuation except as noted below:
 - o Any other grade 3 non-skin, drug-related AE lasting >7 days including fatigue.

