4.9 Criteria for Removal from Treatment

Participants will be removed from study when any of the applicable criteria, including PD, AEs, participant withdrawal, or inability to follow study protocol as listed in Section 4.7.

The reason for study removal and the date the participant was removed must be documented in the Case Report Form.

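### The last sentence of Section 4.2.1 tells sites to keep treating non-progressors who have ECOG above 2 or discontinuation-level toxicity, contradicting the protocol's own stop rules

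*Combined protocol and SAP*

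**What the plan says.** Section 4.2.1 (Dosing for Stratum 1) contains two rules for the same participants.

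- The second paragraph makes further study drug conditional. From the week 8 response visit on, a participant without confirmed progression may continue only if ECOG is 2 or lower and he or she "did not have a DLT or other safety risk requiring discontinuation of the study drugs".
- The closing sentence of the next paragraph covers people who fail those conditions. Without confirmed progression after four cycles, participants with ECOG above 2 or "toxicity requiring discontinuation of the study drugs will continue treatment until confirmed PD, requiring initiation of a new treatment".

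Section 4.2.2 enrols Stratum 2 at the Stratum 1 MTD "following the dose de-escalation rules and treatment plan outlined above in Section 4.2 and 4.2.1", so the closing sentence applies there too.

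Elsewhere the protocol says to stop:

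- Sections 4.2 and 4.2.2: "participants who have dose limiting AEs or disease progression will discontinue therapy".
- Table 1 footnote in Section 4.2: "Treatment will continue until documented disease progression, discontinuation due to toxicity, withdrawal of consent, or the study ends".
- Section 4.7 ends therapy for a list of unacceptable adverse events, beginning with "Any grade 4 events except as noted below".
- Section 4.9: "Participants will be removed from study when any of the applicable criteria, including PD, AEs, participant withdrawal" or inability to follow the protocol, with reference to Section 4.7.
- Section 5.1 repeats the two continuation conditions of Section 4.2.1.

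Section 4.2.3, the parallel text for the expansion cohorts, ends with "Participants with a confirmed PD will discontinue the study drugs" and has no counterpart to the disputed sentence.

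**The concern.** A site that reads the closing sentence as written would go on giving nivolumab, with or without ipilimumab, to someone whose toxicity already requires stopping or whose performance status is worse than the protocol allows. The sentence is also the most specific rule on the subject: it names these two groups and says what happens to them. A site could therefore take it as an exception to the general stop rules.

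The stake is individual safety. The Section 6.1 risk lists warn of severe and possibly fatal immune-mediated events with both drugs, and Section 5.1 notes that myocarditis has caused deaths. Section 5.2.3 puts the usual onset of ipilimumab immune-related events at 3 to 10 weeks after the first dose. That interval includes week 8, when the sentence takes effect.

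**Working it through.** The plan gives no statistic to reproduce for the contradiction itself. The check sets the texts side by side and then bounds the exposure and the reach.

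**1. What treatment means in the sentence.** Earlier in the same paragraph, continuing treatment is counted in cycles, up to 46. The plain reading is study drug, not follow-up.

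**2. The ECOG limb.** The closing sentence says ECOG above 2 continues. The preceding paragraph of 4.2.1 and Section 5.1 require ECOG of 2 or lower. The conflict is direct. Section 4.7 has no ECOG criterion, only investigator-judgment criteria that could cover it, so the explicit limit rests on 4.2.1 and 5.1 alone.

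**3. The toxicity limb.** The closing sentence says toxicity requiring discontinuation continues. Section 4.2, the Table 1 footnote, the preceding paragraph of 4.2.1, and Sections 4.2.2, 4.7, 4.9 and 5.1 all say stop. The limb also contradicts itself, since toxicity that requires stopping the drugs cannot go with continuing them.

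**4. Precedence.** The only ranking in Section 5.1 places it above Appendix X. Nothing ranks 4.7 or 5.1 above 4.2.1.

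**5. DLT counts.** Four cycles × 2 weeks = 8 weeks. The DLT window in Section 4.4 is 6 weeks from the first dose. The sentence takes effect after the window closes.

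**6. Maximum further exposure for one participant.**
- Nivolumab: 46 − 4 = 42 infusions, and 42 × 2 = 84 weeks. This reproduces the Synopsis figures for treatment after week 8.
- Ipilimumab, dose level 2: cycles 7 to 46 in steps of 3, (46 − 7)/3 + 1 = 14 of the 16 doses.
- Ipilimumab, dose level −2: cycles 7, 13, 19, 25, 31, 37 and 43 = 7 of the 8 doses.

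**7. Reach.**
- Section 2.3.9, dated April 2019, reports dose level 2 as tolerable in Stratum 1. Assuming Stratum 1 enrolment was complete by 30 April 2019, the 92-week maximum ends on 2 February 2021. The current document is Version 15.0 of 24 August 2023, so Stratum 1 dosing has probably ended.
- Section 10.2 caps Stratum 2 at 18. Only those without confirmed progression who have ECOG above 2 or stopping-level toxicity after four cycles are affected. The documents do not count them, and do not say whether any Stratum 2 participant is still on drug.
- Section 4.2.3 borrows the strata's treatment schedule for the combination expansion cohort but states its own continuation rule. I take that rule to govern, so the expansion cohorts are outside the reach.

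**The case against.** The strongest case on the other side is that this is a slip no careful site would act on. The toxicity limb cannot be carried out as written, because the clause itself says the drugs must stop. Section 4.2.1 also requires continued eligibility to be determined and documented before dosing at response visits, and dosing at ECOG above 2 or after a safety stop should fail that check. Nothing shows that anyone on treatment is exposed.

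Most of this stands, and it lowers the likelihood and reach. It does not remove the error. The ECOG limb can be carried out, and no text reconciles it with the limit. The documented check is tied to reviewing response results, and a site would apply it with the closing sentence in front of it.

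Three stronger readings are tempting, and the documents do not support them.

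- A reader might infer that affected participants would receive 42 more infusions. That is a theoretical maximum. It ignores the limits on treatment delay in Sections 4.5, 4.10 and 5.1 (35, 42 or 56 days, depending on regimen and steroid taper) and the stop after more than two delays for the same event.
- A reader might infer that the MTD is compromised. Step 5 rules that out for this sentence.
- A reader might infer that Section 5.1 should be rewritten to match the Section 4.7 stops for systemic steroids and for grade 3 events lasting more than 7 days. Several 5.1 rows do differ from 4.7: some provide for steroids and later resumption, and some grade 3 rows set no 7-day limit. But Sections 4.5, 4.10 and 5.1 allow up to 56 days for a steroid taper, 4.10 encourages early steroids with a view to restarting, and 4.4 and 5.2 send management decisions to Section 5. Which text should yield is a clinical choice that the documents do not settle.

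**Conclusion.** The contradiction is real, and the sentence is wrong as written. It is best classed as a drafting inconsistency with a safety consequence, not as a statistical or design fault. It is probably a slip: the parallel text in Section 4.2.3 lacks it, and the likely intent was to stop drug and keep following these participants until progression or new treatment. That intent is an inference from context; the text does not state it.

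The size is small in numbers and potentially serious for an individual. Live reach is at most an uncounted subset of Stratum 2's ceiling of 18, and may be nobody. This rests on Stratum 1 enrolment having finished by April 2019 and on Section 4.2.3 governing the expansion cohorts. No effect on DLT counts, the MTD or any estimate is claimed. The correction is still worth making because current text directs dosing in participants whom the rest of the protocol takes off drug.

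**What to change.** Replace the last sentence of Section 4.2.1 with:

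*Participants without confirmed progression who have ECOG >2 or toxicity requiring discontinuation will discontinue the study drugs and be followed, with the Section 8.7 assessments, until confirmed PD, start of a new treatment, or the end of follow-up in Section 4.8, whichever comes first.*

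The last endpoint is needed because Section 4.8 ends routine follow-up at 16 weeks, before many of these participants would progress. Anyone removed for an unacceptable adverse event is still followed to resolution or stabilization under 4.8.

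Send sites a short memo, and check whether any Stratum 1 or Stratum 2 participant was dosed after cycle 4 under the present wording.

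The cost is one amended sentence, a memo and a limited data check. No procedures are added, because Section 8.7 already schedules visits at 6 and 16 weeks after the last dose with response assessment.

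Separately, the study chairs should reconcile the systemic-steroid and 7-day stops in Section 4.7 with the Section 5.1 rows and the 56-day taper allowances. That is a clinical decision and should not hold up this correction.
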